7.3.2.1. Handling of Missing Date Values

Partial or Missing Dates

The following conventions will be used to impute missing portions of dates for AEs and concomitant medications, if warranted. Note that the imputed values outlined here may not always provide the most conservative date. In those circumstances, the imputed value may be replaced by a date that will lead to a more conservative analysis.

A. Start Dates

- 1) If the year is unknown, then the date will not be imputed and will be assigned a missing value.
- 2) If the month is unknown, then:
 - i) If the year matches the first dose date year, then impute the month and day of the first dose date.
 - ii) Otherwise, assign 'January.'

- 3) If the day is unknown, then:
 - i) If the month and year match the first dose date month and year, then impute the day of the first dose date.
 - ii) Otherwise, assign the first day of the month.

B. Stop Dates

- 1) If the year is unknown, then the date will not be imputed and will be assigned a missing value.
- 2) If the month is unknown, then assign 'December.'
- 3) If the day is unknown, then assign the last day of the month.

7.3.2.2. Missing Baseline Data

Every effort will be made to ensure that accurate baseline information on the subjects is collected. In the event that a subject is missing baseline information, the subject will be included in the SP for assessment of safety and excluded from the primary analyses. Each case of missing baseline data will be evaluated for potential inclusion in the exploratory endpoints. All baseline data will be observed cases, without imputation.

7.3.2.3. Imputation Methods

[REDACTED]

[REDACTED]

[REDACTED]

[REDACTED]

The imputations will be done separately for each treatment group and will include the following variables in the imputation model: mLcVA at baseline and Day 8.

The number of imputations [REDACTED]. The change from baseline will be calculated from these imputed datasets. The observed outcome ([REDACTED]) for each imputed dataset will be [REDACTED]. See [Section 9.1](#) for details on these models. The estimates

and standard errors (SEs) of the odds ratios based on the

Example SAS code is provided below:

7.3.3. Handling of Early Termination Visit Information

In the event that a subject is terminated early from this study, the early termination data for safety and efficacy variables will be assigned to the closest visit (Day 8 or Day 15). If the closest visit has valid data, the early termination data will be assigned to the next available visit.

7.3.4. Pooling of Investigational Sites

The data from all study centers will be pooled together for all planned analyses.

7.3.5. Coding Conventions for Events and Medications

All AEs and medical history will be mapped to the Medical Dictionary for Regulatory Activities (MedDRA Version 23.1) system for reporting (preferred term and body system).

Prior and concomitant medications will be coded using WHO-DD (World Health Organization Drug Dictionary) (Global Version 2020-09-01).

7.3.6. Analysis Software

Data manipulation, tabulation of descriptive statistics, calculation of inferential statistics, and graphical representations will be performed primarily using SAS (release 9.4 or higher) for Windows. If the use of other software is warranted, the final CSR will detail what software was used and for what purposes.

[figure not shown]
7.3.7. Study Data

Study data identified in the schedule for time and events ([Table 1](#)) are collected, and source verified, on the electronic data capture (EDC) MedNet version 1.212.2.

All study data will be formulated into regulatory-compliant data sets to provide transparency, traceability, and integrity of trial analysis results from the collection source. Observed study data will be mapped to the Clinical Data Interchange Standards Consortium (CDISC) Study Data Tabulation Model (SDTM) and serve as the source data from the trial. All study analyses will be completed using analysis data sets that are derived from the SDTM and follow the CDISC Analysis Data Model (ADaM) architecture.

The methods for programming the CDISC SDTM and ADaM data sets are described in [Figure 1](#).

Figure 1 SDTM, ADaM, and TFL Development and Validation

7.4. Planned Study Analyses

7.4.1. Statistical Summaries: Descriptive and Inferential

Categories for data presentation and analysis will consist of each treatment group (Nyxol or Placebo).

All statistical tests will be two-sided and a difference resulting in a p-value of less than or equal to 0.05 will be considered statistically significant. All p-values will be rounded to and displayed in four decimals. If a p-value less than 0.0001 occurs, it will be shown in tables as <0.0001.

Descriptive summaries of variables will be provided where appropriate. For continuous variables, the number of non-missing values (n), mean, standard deviation, median, minimum, and maximum will be tabulated by treatment group. For categorical variables, the counts and proportions of each value will be tabulated by treatment group. Expansion of descriptive table categories within each treatment may occur if such elaborations are thought to be useful.

All study-related data collected will be presented in listings. Study-related data not subject to analysis according to this plan will not appear in any tables or graphs but will be included in the data listings.

7.4.2. Interim Analyses and Data Monitoring

No formal interim analysis or safety monitoring committee is planned for this study.

7.4.3. Final Analysis and Publication of Study Results

The final analysis will be completed after all subjects have completed the study.

7.5. Multiple Testing Procedures

There will be no adjustments for multiplicity and no formal multiple testing procedures are to be implemented with this analysis plan.

7.6. Baseline Values

Baseline values are the values obtained prior to any drug administration on the evening of the Baseline Visit (Day 1). If the Day 1 value is missing, any value collected prior to treatment administration will be treated as the baseline.

8. SUMMARY OF STUDY DATA

8.1. Subject Disposition

A summary of the analysis sets includes the number and percentage of subjects by treatment group and overall for the following categories: subjects in the ARP, subjects in the SP, subjects in the mITT Population, and subjects in the PP Population. All percentages will be based on the number of subjects in the ARP.

End of trial information will also be summarized in this table, including the number of subjects completing the study, the number of subjects who prematurely discontinued the study with reasons for withdrawal, , and the number of subjects who prematurely discontinued the study medication with reasons for study medication discontinuation.

A by-subject data listing of study completion information including the reason for premature study withdrawal, if applicable, will be presented.

8.2. Protocol Deviations

Major protocol deviations considered to have significant impact on treatment outcome, as determined by a Sponsor blinded review of the data prior to database lock and unblinding of the study, may result in the removal of a subject's data from the PP Population. The Sponsor or designee will be responsible for producing the final deviation file; this file will include a description of the protocol deviation and clearly identify whether this violation warrants exclusion from the PP Population. This file will be finalized prior to database lock.

All protocol deviations will be presented in a by-subject data listing, with a flag to indicate if a deviation was considered major.

8.3. Demographics and Baseline Characteristics

Subject demographic data and baseline characteristics will be tabulated and summarized descriptively by treatment group and overall. The demographic data and baseline characteristics will be summarized for the mITT Population, PP Population, SP, and ARP. If the mITT population is equivalent to any of the other populations, then only the mITT version will be generated rather than repeating equivalent summaries.

The demographics consist of age (year), sex, race, ethnicity, and study eye, iris color (light blue, dark blue, blue with peripupillary brown, uniform green, green with brown iris ring, central brown and peripheral green, brown with some peripheral green, or brown), irides type (light or dark), and eyeglasses-wearing status (yes or no; distance vision or near vision). A subject's age in years is calculated using the date of the informed consent and date of birth. Age will be summarized using descriptive statistics. The number and percentage of subjects by sex, race, ethnicity, study eye, iris color, irides type, and distance vision/near vision correction status, will also be reported. Percentages will be based on the total number of subjects in the study population presentation.

The following baseline characteristics will be summarized for study eye and non-study eye, and for binocular for visual acuity assessments, using descriptive statistics:

- mLCHA
- pLCVA
- mLCHA
- DCNVA
- Pupil diameter (photopic and mesopic)
- IOP
- Total RMS error (score)
- Total wavefront higher-order error (score)
- Higher-order RMS (spherical, coma, trefoil) error

All demographic and baseline information will be presented in by-subject listings.

8.4. Medical History

The number and percent of subjects with individual medical histories will be summarized for all subjects by treatment group and overall. Non-ocular and ocular medical history will be summarized separately.

Medical history will be coded using the MedDRA Version 23.1. The number and percentage of subjects with any medical history will be summarized overall and for each system organ class (SOC) and preferred term (PT). Percentages will be calculated based on number of subjects in the SP.

Subject medical history data including specific details will be presented in by-subject listings.

8.5. Prior and Concurrent Medications

The number and percentages of all concomitant medications will be summarized by treatment group, Anatomical Therapeutic Chemical (ATC) level 4, and PT. The total number of concomitant medications and the number and percentages of subjects with at least 1 concomitant medication will be summarized by treatment group. All summaries will be performed using the SP.

A concomitant medication is defined as any medication taken on or after the day of first exposure to study drug.

Prior medications are defined as any medication that has a start and stop date prior to the day of first exposure to any study drug, collected from up to 30 days prior to Screening. The total number of prior medications and the number and percentages of subjects with at least 1 prior medication will be summarized by treatment group.

8.6. Treatment Exposure and Compliance

[REDACTED]

9. EFFICACY ANALYSES

Unless otherwise noted, efficacy will be assessed using the mITT and PP populations, with subjects included in their randomized treatment regardless of the treatment they actually received. For the analysis of the primary efficacy endpoint, imputation will be performed for missing data as described in [Section 7.3.2.3](#). If the analysis using the mITT Population shows a positive effect for Nyxol at the 0.05 level of significance, the primary endpoint will be considered met.

Confirmatory analysis of the primary efficacy endpoint will be performed using the ARP, also using imputation for missing data. For the analysis of the secondary efficacy endpoints, only observed case data will be used.

To formally test the significance of endpoints of interest beyond primary efficacy, endpoints will be tested in a predefined sequence using observed data only, each at the significance level 0.05, until the first nonsignificant test. The primary efficacy endpoint will be first in this sequence. The endpoints in the sequence are for the mITT population and study eye, and either Day 8 or Day 15. The sequence is specified in [Section 12.3](#).

All efficacy assessment data, regardless of whether they are included in the analysis, will be presented in by-subject listings.

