7.1.1. Modified Intention-to-Treat (mITT)

The mITT will include all randomized subjects who received at least 1 dose of study medication and have a Baseline and any Day 8 efficacy measurement. The mITT will be used for the primary endpoint analysis and to analyze efficacy endpoints, with subjects included in their randomized treatment regardless of the treatment they actually received.

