7.3.2. Missing Data

The primary efficacy endpoint is the percent of subjects with ≥ 15 ETDRS letters (≥ 3 lines) of improvement in the study eye compared to baseline in monocular mLcVA at Day 8. For the analysis of the primary efficacy endpoint, imputation will be performed for missing efficacy data as specified in [Section 7.3.2.3](#) for the analysis using the mITT. Confirmatory analyses will be performed using the ARP, also using imputation for missing data.

Otherwise, there will be no substitutions made to accommodate missing data points for efficacy data. All data recorded on the CRF will be included in data listings that will accompany the CSR.

Safety data will be imputed in limited situations. If the severity of an AE is missing, then the severity will remain missing. If relationship of the AE to study drug is missing, the relationship will remain missing. Missing or partial dates for AEs or concomitant medications will be imputed as described in [Section 7.3.2.1](#). Otherwise, all summaries of safety endpoints will be completed using observed cases in the SP; no imputation will be completed.

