9.1.2. Secondary and Exploratory Efficacy Analysis

Secondary and exploratory efficacy endpoints are indicated in [Section 4.2.2](#). Secondary and exploratory efficacy endpoints will be analyzed by study eye, non-study eye, the best of either eye, and binocular, unless otherwise indicated.

Visual acuity assessments (mLCVA, pLCVA, mHCVA, and DCNVA) will be summarized using letters. For mLCVA, pLCVA, and mHCVA, the assessments will also be summarized using logMAR units. Only letters will be recorded in the CRF. Letters will be converted to logMAR using the following formula: $\text{logMAR} = 0.02 * (\text{S} - \# \text{ Letters})$, where $\text{S} = 55$. The values of S are the number of letters read equivalent to a Snellen Acuity of 20/20. For example, for mLCVA, if the # letters = 55, then $\text{logMAR} = 0.02 * (55 - 55) = 0.00$; if # letters > 55, then logMAR is negative.

Each of the continuous secondary efficacy endpoints will be analyzed using analysis of covariance (ANCOVA), with change from baseline as the dependent variable, treatment, and [REDACTED] and the respective baseline value included as the covariate.

Each ANCOVA will be performed using the mITT and PP populations. The output from each ANCOVA will include the LSM and SE for both treatment groups, along with the placebo-corrected LSM, its 95% CI and associated p-value.

For each of the secondary endpoints related to percent of subjects achieving certain criteria, the analysis will be performed using a logistic regression model with treatment [REDACTED] [REDACTED]s, and the respective baseline as a covariate. For each analysis, the percentage of subjects in each treatment group meeting the criteria, the OR with 95% CI and p-value will be provided.

In addition, each secondary efficacy endpoint will be analyzed by [REDACTED] the same model indicated above but without irides as a factor.

For Day 8 and Day 15, the time since last dose of study treatment will be calculated as follows: date/time of visit minus date/time of the most recent dose of study medication in the subject diary. [REDACTED]

[REDACTED] For each subject, the category could be different for Day 8 and Day 15. Summaries of improvement in mLCVA, and change and percent change in pupil diameter, will be presented based on these categorizations.

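### Day 15 endpoints in the formal test sequence are tested on observed cases with models that ignore the Day 8 value, so loss after Day 8 that depends on response and differs by arm would bias them in either direction.

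*SAP*

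**What the plan says.** SAP Section 9 sets up fixed-sequence testing beyond the primary endpoint: "endpoints will be tested in a predefined sequence using observed data only, each at the significance level 0.05". On scope it adds: "The endpoints in the sequence are for the mITT population and study eye, and either Day 8 or Day 15". Section 7.4.1 makes every test two-sided at 0.05.

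The missing-data rule for these endpoints appears twice. Section 9 states: "For the analysis of the secondary efficacy endpoints, only observed case data will be used". Section 7.3.2, after providing imputation for the primary endpoint, states that otherwise "there will be no substitutions made to accommodate missing data points for efficacy data".

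On the model, Section 9.1.2 states: "Each of the continuous secondary efficacy endpoints will be analyzed using analysis of covariance (ANCOVA), with change from baseline as the dependent variable". The respective baseline is the covariate. Responder endpoints use logistic regression, also with baseline. Part of the model text is blacked out; nothing visible uses the Day 8 value for a Day 15 endpoint.

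Two further rules matter. The SAP's mITT (Section 7.1.1) takes randomized subjects who "received at least 1 dose of study medication and have a Baseline and any Day 8 efficacy measurement". Section 7.3.3 sends early termination data to the closest visit and then says: "If the closest visit has valid data, the early termination data will be assigned to the next available visit".

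**The concern.** An observed-case comparison at Day 15 is unbiased if, given arm and baseline, leaving between Day 8 and Day 15 is unrelated to the outcome. That is doubtful here, because a subject's experience in the first week can drive the decision to stop. Protocol Section 4.9.1 lists adverse events and perceived lack of efficacy among the reasons for stopping.

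Every mITT subject who lacks Day 15 has some Day 8 efficacy measurement, though not necessarily of the endpoint being tested. The planned test makes no use of it.

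The status of these tests has also changed. Protocol Section 9.3.1 treated secondary p-values as descriptive. SAP Section 3.3 records that a hierarchical analysis was added to test further endpoints formally, but the observed-case rule stayed. What is at stake is the size of a Day 15 effect, any claim of durability that rests on it, and the error rate at that step of the sequence.

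**Working it through.** **The plan's own figure.** SAP Section 6: 136 evaluable subjects and 15% drop-out between Day 1 and Day 15. 136 / (1 − 0.15) = 160, which matches the planned total. The allowance is 160 − 136 = 24 subjects. The documents do not split it by visit or arm, so between 0 and 24 could leave after Day 8. Since evaluable means having a Day 8 value (Protocol 9.1, SAP 5.1), a literal reading puts all 24 before Day 8; the SAP's Day 1 to Day 15 wording allows them after it.

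**Continuous endpoint.** Assumptions, none from the documents: 80 per arm with a Day 8 value, SD 8 letters, correlation ρ between Day 8 and Day 15 of 0.5 or 0.7. A fraction d of each arm is lost after Day 8. One arm loses only from its worse half at Day 8, the other at random. The baseline covariate is left out for simplicity.

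The worse half of a normal distribution averages √(2/π) = 0.798 SD below the mean. Removing a fraction d from it raises the mean of those who remain, so the bias at Day 15 is

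bias = ρ × SD × 0.798 × d / (1 − d).

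Example with ρ = 0.7 and d = 0.15 (12 of 80 per arm, 24 in all): 0.7 × 8 × 0.798 × 0.15/0.85 = 0.79 letters. The standard error is 8 × √(2/68) = 1.37, so the chance of a false positive for that arm is P(Z > 1.96 − 0.79/1.37) = about 8%, against 2.5% nominal.

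Simulation with no true effect, 3,000 runs per row:

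| d | ρ | Formula bias | Observed-case bias | Bias using Day 8 | False positive for that arm |
|---|---|---|---|---|---|
| 5% | 0.5 | 0.17 | 0.12 | −0.04 | 3.0% |
| 5% | 0.7 | 0.24 | 0.19 | −0.04 | 3.1% |
| 10% | 0.5 | 0.35 | 0.39 | 0.04 | 4.8% |
| 10% | 0.7 | 0.50 | 0.50 | 0.01 | 5.9% |
| 15% | 0.5 | 0.56 | 0.54 | −0.01 | 5.3% |
| 15% | 0.7 | 0.79 | 0.79 | 0.02 | 8.4% |

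The Day 8 column is a likelihood estimate of the kind a repeated-measures model gives.

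**Direction.** True difference 4.0 letters, d = 15%, ρ = 0.7:

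| Arm losing its poor responders | Observed cases | Using Day 8 |
|---|---|---|
| Nyxol only | 4.76 | 3.98 |
| Placebo only | 3.18 | 3.97 |
| Both alike | 4.00 | 4.01 |

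**A heavier rule.** 75 per arm, SD 7, ρ = 0.75, true difference 4.0. Subjects with a Day 8 gain under 3 letters leave with probability 0.3 to 0.4, others with 0.03 to 0.05. The mean Nyxol gain is varied from 4 to 8 letters.
- Rule in Nyxol only, placebo losing 5% at random: 4.5 to 4.9.
- Same rule in both arms: 3.7 to 4.0. Placebo, with the smaller gain, has more subjects under the cut-off and loses more of them.
- Rule in Nyxol only, half of the leavers having an early termination value that stands for Day 15: 4.2 to 4.4.
- Estimate using Day 8: about 4.0 throughout.

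At a mean gain of 4, the share under 3 letters is Φ((3 − 4)/7) = 0.443. Nyxol loss is then 0.443 × 0.3 + 0.557 × 0.03 = 15%, up to 0.443 × 0.4 + 0.557 × 0.05 = 21%.

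**Responder endpoint.** If true rates p are equal and one arm loses only non-responders, its observed rate becomes p / (1 − d). At d = 15%: 0.10/0.85 = 11.8%, 0.20/0.85 = 23.5%, 0.30/0.85 = 35.3%. These are false differences of 1.8, 3.5 and 5.3 points. With 80 × 0.85 = 68 observed per arm, the chance of a false positive for that arm is 5.2%, 7.2% and 9.6%. At d = 5% (76 per arm) the differences are 0.5, 1.1 and 1.6 points and the chances 3.2%, 3.6% and 4.0%.

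**The case against.** The strongest reply is SAP Section 7.3.3. A subject who leaves after Day 8 and has an early termination assessment gets a Day 15 value and stays in. A reader might infer from the observed-case rule that everyone who leaves after Day 8 is dropped; the documents do not support that. Still, the safeguard looks thin. Protocol Section 4.5 lists three clinic visits and a telephone call, with no early termination visit. After withdrawal of consent or non-compliance, Section 4.9.4 asks for the Day 8 measurements and a call, and Section 7.2.5 asks for telephone follow-up of early discontinuers. SAP Section 7.3.1 keeps unscheduled-visit data out of the analysis. How often Section 7.3.3 would supply a Day 15 value cannot be told.

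A reader might also infer that the plan inflates the Nyxol effect. That needs poor responders to leave mainly from Nyxol. The trial is double-masked and lack of efficacy is not specific to an arm. The same cut-off rule in both arms gives no bias or a bias against Nyxol. This objection stands: direction is not a property of the plan.

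Third, the 15% covers the whole study, so loss after Day 8 may be near zero. That stands too, and the size above is conditional on it. With 10% lost at random, neither method is biased and using Day 8 lowers the standard error by only about 3%.

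Fourth, Protocol Section 9.3.5 allows imputed analyses of secondary endpoints in the all-randomized population if warranted. That is optional, and the visible SAP text does not plan one.

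Finally, SAP Section 7.5 still says that no formal multiple testing procedure is used. Sections 3.3 and 9 say otherwise, and this point relies on them.

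**Conclusion.** The point holds in a conditional form. Day 15 endpoints in the sequence are tested at 0.05 on observed cases, with visible models that leave out the Day 8 value. Subjects who leave after Day 8 without an early termination efficacy assessment are excluded despite having Day 8 data.

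The bias needs two things together: loss that depends on response, and a difference between arms in that loss. Under the settings above, a true 4.0 letters is estimated anywhere from about 3.2 to 4.9. With no true effect, the chance of a false positive for the favoured arm on a continuous endpoint is about 3% at 5% loss and 5 to 8% at 15%, against 2.5%. The bias is about zero when loss is random or takes the same share of poor responders from each arm.

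The SDs, correlations, loss rates and leaving rules are assumptions. So is the presence of Day 15 endpoints, continuous or responder, in the sequence: Section 9 points to some, but the list in Section 12.3 is not visible. The Day 8 primary endpoint is not touched. This is a worthwhile, inexpensive improvement, not a threat to the trial's main claim.

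**What to change.** In SAP Sections 9 and 9.1.2:
- For continuous endpoints in the sequence, prespecify one repeated-measures model with treatment, visit, treatment by visit, baseline by visit, the stratification factor (iris color) and unstructured covariance. Take the Day 8 and Day 15 contrasts from it.
- For Day 15 responder endpoints in the sequence, use multiple imputation by arm that includes baseline and Day 8, then the planned logistic regression.
- Keep the observed-case ANCOVA and logistic regression as supporting analyses.
- Add a sensitivity analysis for data not missing at random, since the Day 8 value cannot account for loss driven by what happens after it.
- State how early termination values assigned under Section 7.3.3 enter these models, and report by arm how many Day 15 values come from that rule.

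The cost is SAP wording, modest programming and some extra output, all before unmasking. The new analysis relies on data being missing at random given Day 8, which is a weaker assumption than the observed-case analysis makes. In every scenario run it was no worse on bias or standard error.
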